Title:

Pain perception with cervical tenaculum placement during office procedures: A randomized controlled trial

Authors:

[name]; [name] MS, [name]

ClinicalTrials.gov

NCT ID: NCT02969421

Protocol Date:

December 22, 2016

Introduction

Gynecology is undergoing a transformation in the location of care delivery. As a result of technological innovations, procedures are migrating from the hospital and ambulatory surgical center to the office setting. There are numerous advantages to office-based procedures. They include reduced patient expenses, improved scheduling convenience, favorable provider reimbursement, enhanced continuity of care, and patient satisfaction.¹ However, success of office-based procedures is based on numerous factors such as patient selection, physician competency, teamwork and communication, along with adequate and safe anesthesia.²

The goal of most office-based procedures is twofold: (1) to be able to safely and successfully perform the procedure, and (2) patient comfort. The experience of pain is influenced not only by physical factors but also by psychological and social factors. Regardless of procedure type, anxiety, depression, and a woman's anticipation of the pain she will experience are strong predictors of the pain experienced during office gynecologic procedures. For procedures that involve cervical dilation and passage of a device or cannula through the internal os of the cervix, a history of dysmenorrhea, nulliparity, and postmenopausal status are associated with increased pain.³

The importance of patient counseling and patient selection remains pivotal in success of in-office procedures.⁴ Numerous studies have focused on optimal pain control during in-office procedures analyzing analgesia, anesthesia, anxiolytics, combination regimens, local anesthesia, and nonpharmacologic techniques. The indisputable evidence thus far supports the idea that a multimodal approach may be most effective in achieving adequate pain control.^{3,4} However, what steps can we take with our procedural methods to further improve patient comfort.

In most gynecologic procedures involving cervical and uterine instrumentation, the single-toothed tenaculum is used for stabilization and traction, and allows descent of the uterus within the speculum. Most importantly, the tenaculum decreases the flexion of the uterus and eases passage of instruments into the endometrial cavity. Tenaculum placement generally precedes insertion of intrauterine devices, removal of intrauterine devices, endometrial biopsy, uterine aspiration, and hysteroscopy. Despite the very frequent use and importance of the tenaculum, few studies directly compare methods to decrease pain with tenaculum placement.³

Commonly described strategies for tenaculum placement include slow placement of the tenaculum, having the patient cough while the tenaculum is placed, use of atraumatic tenaculums, and/or application of local anesthetics.³

Doty et.al published a randomized control trial of 80 women randomized to the use of vulsellum or a single-tooth tenaculum during IUD insertion. Their primary outcome was reported pain. They found pain scores at the time of tenaculum placement to be the same in both groups.⁵

Goldthwaite et.al investigated the effect of local anesthetics on pain at the time of tenaculum placement. Seventy-four women were randomized to receive 1% lidocaine intracervical injection or topical application of 2% lidocaine gel to the cervix immediately prior to tenaculum placement. The primary outcome was pain at time of tenaculum placement. They found that women who received injection had lower mean pain levels at tenaculum placement but higher mean pain levels with study drug application. Both outcomes were statistically significant.⁶

The two commonly described strategies for tenaculum placement, slow versus having the patient cough while the tenaculum is placed are utilized by providers based on preference and/or their previous training. There is no published study that compares these methods to one another. Doty and Goldthwaite utilized each method separately. In Doty's study that compared tenaculum type, patients were asked to cough at time of vulsellum or single-tooth tenaculum placement, no local or systemic analgesic was used, and pain was measured using a 100-mm visual analog scale.⁵ In Goldthwaite's study that compared lidocaine injection versus jelly, the tenaculum was closed slowly over 3 seconds and pain was rated using a 100-mm visual analog scale.⁶ Our study aims to compare these strategies, slow tenaculum placement versus the cough method, and their effects on pain at time of placement. Provider satisfaction with tenaculum placement will be measured as a secondary outcome. Overall pain with IUD insertion will also be a secondary outcome. I hypothesize that slow tenaculum placement is less painful to patients and offers higher provider satisfaction scores.

Methods and Materials

Randomized controlled trial from December 2016 to April 2017 at Duke University Medical Center Gynecology Clinics.

Data to be collected from each subject prior to randomization:

- Age
- Parity
- Race
- Highest education level achieved
- Number of cesareans
- BMI
- History of chronic pain
- Daily narcotic use
- GAD7 Score

Inclusion criteria:

- Women ages 18 years and older
- Undergoing IUD placement
- English or Spanish speaking

Exclusion criteria:

- Primary language other than English or Spanish

Sample size determination

Visual analog scale (VAS) is a continuous scale comprised of a horizontal or vertical line, usually 10 centimeters (100 mm) in length, anchored by 2 verbal descriptors, one for each symptom extreme. For pain intensity, the scale is most commonly anchored by “no pain” (score of 0) and “worst imaginable pain” (score of 100). The respondent is asked to place a line perpendicular to the VAS line at the point that represents their pain intensity. Using a ruler, the score is determined by measuring the distance (mm) on the 10-cm line between the “no pain” anchor and the patient’s mark, providing a range of scores from 0-100. The following cut points on the pain VAS have been recommended: no pain (0-4 mm), mild pain (5-44 mm), moderate pain (45-74 mm), and severe pain (75-100 mm).⁷ Todd et.al in their quest to address the question of clinical significance of VAS scores, found that 13 mm is the minimum mean change on a standard 100-mm visual analog pain scale that should be considered clinically significant for acute, traumatic pain.⁸ This finding was later validated in a prospective, observational cohort study by Gallagher et.al.⁹

We have chosen a 16 mm difference on a standard 100-mm visual analog pain scale as value of clinical significant. In order to detect at least a 16 mm difference with 90% power and alpha of .05, we estimated a total sample size of 66.

Randomization:

All patients meeting study criteria will be randomized using computer generated random numbers (randomization.com). This is not a blinded study so patients and providers will be aware of the group each subject is randomized to. This randomization will be revealed prior to speculum placement.

Procedure at time of IUD insertion:

A single-tooth tenaculum will be used in placement of all IUDs. Each subject will be placed in the standard dorsal lithotomy position. To start data collection, each subject will be asked to rate their baseline pain. After speculum placement, and adequate visualization of the cervix by the provider, the subject will be asked to rate their pain using a 100-mm visual analog scale. The provider will then place the tenaculum on the anterior lip of the cervix closing to the first ratcheted click over a 5 second period. At this point, the subject will be asked to rate their pain using a 100-mm visual analog scale. If the subject was randomized to the cough arm, the subject will be asked to give one strong cough. This first cough will serve as a test cough. If provider is pleased by the strength of the patient’s cough, the subject will then be asked to cough again and at this cough the tenaculum will be placed on the anterior lip of the cervix. Only one test cough will be allowed. At this point, the subject will be asked to rate their pain using a 100-mm visual analog scale. All subjects will be asked to rate their overall pain at the completion of the procedure. The provider will be asked to rate their satisfaction with tenaculum placement on a Likert-type 5 point satisfaction scale. 1: not at all satisfied, 2: slightly satisfied, 3: moderately satisfied, 4: very satisfied, 5: extremely satisfied.

A script will be read by the provider during the process of IUD insertion. The script reads as follows.

Provider Says: First, we will place each foot in its footrest. Please lay back and slide your bottom downward towards me. I will tell you when to stop. On your scoring sheet, please mark your pain at this time.

Provider does: Place speculum and achieve adequate visualization of the cervix.

[figure not shown]
Provider says: On your scoring sheet, please mark your pain at this time.

Provider does: Clean cervix. Place tenaculum on anterior lip of cervix in accordance to your randomized group.

[figure not shown]
Slow Method

The tenaculum is to be placed on the anterior lip of the cervix.

After visualization of the anterior lip of the cervix, open the tenaculum and close it slowly over 5 seconds to the first ratcheted click. No more than 1 cm of cervix should be grasped between your tenaculum teeth.

Maximum amount of cervix to grasp

Too much cervix grasped

Cough Method

The tenaculum is to be placed on the anterior lip of the cervix.

After visualization of the anterior lip of the cervix, ask the patient to give a strong cough. If you are pleased with the cough (cervix remained in view during cough), then ask the patient to cough once more. During the cough, the open tenaculum should be closed on the anterior lip of the cervix to the first ratcheted click. No more than 1 cm of cervix should be grasped between your tenaculum teeth.

Provider says: On your scoring sheet, please mark your pain at this time.

Provider does: Sound uterus, place IUD, cut strings, remove speculum.

Provider says: On your scoring sheet, please mark your pain at this time.

Subject Compensation – Subjects will be given \$10 incentive for participation in this study.

Consent Process – Participants will be given adequate time for consent, will be consented in private areas, and will not receive undue influence from study staff to participate. They will be told that declining to participate will not affect their access to healthcare. Steps will be taken to

ensure their privacy. If a participant cannot read the consent or is blind, the consent will be read to them. Subjects who cannot give legal consent will be excluded.

Study Interventions – Not an intervention study. Tenaculum placement will be done as per standard of care procedure.

Risk/Benefit Assessment: No additional risk is placed on the patient by participation in this study as the use of tenaculum is standard procedure. Possible complications include those related to IUD insertion, which is the purpose of their visit. These standard risk include bleeding, infection, uterine perforation, failure of IUD for contraception, need for further procedures at time of removal.

Subjects will be monitored for the standard time after IUD insertion, which is usually until they are able to sit up right and ambulate without lightheadedness or dizziness. Any adverse events will be reported to the IRB per IRB policy. Under this protocol, any time a patient has a post-procedure complication, the attending physician who performed the procedure should be notified. Additionally, we have requested in the consent form that patients contact their provider who performed the procedure, should a complication occur in order to capture patients who may present to outside emergency departments.

There is no direct benefit for any individual subject. The potential knowledge to be gained from this project may make a significant contribution to clinical practice.

Costs to the Subject –Participation will not result in any costs to subjects.

Data collection:

REDCap, web-based password-protected relational database will be created prior to study initiation. All patients consented for the study will have a REDCap generated subject ID code. This code will be used for subject identification. The REDCap database will also store the following information from each subject ID; age, parity, race, level of education, the patient's pain responses, and provider satisfaction.

Statistical analyses:

We will compare groups on the primary outcome of pain using T-tests versus Wilcoxon test pending the normality of the results. We will compare groups on the secondary outcome of provider satisfactions with placement using Chi-square test or Fisher's exact test. We will evaluate for potential correlations based on patient demographics and physician experience.

Privacy, Data Storage & Confidentiality – All paper data will be kept secured in a locked cabinet in [name] office. The data will be retained until the conclusion of the data analysis, then destroyed per IRB guidelines. Only the PI and the personnel listed will have access to the paper data.

During data collection, subject identifiers and relevant data elements will be recorded in the RedCap database. Then, study-specific identification numbers will be assigned to each subject. Prior to dissemination of any information in this database beyond the DUMC's secure servers or firewall, all identifiers will be stripped from the database and data will only be referenced by the study-specific identification numbers. Deidentified data exported from RedCap will be stored in an excel spreadsheet, on a secure network folder managed by the department of Obstetrics and Gynecology in on a secure server behind the Duke University Medical Center firewall. Only study staff listed as key personnel with the IRB will have access to the study folder. The name of the secure network folder will be the same as the IRB protocol number.

A master log, which links the study-specific identification number to the study subject, will be generated. The master log will be stored on the same secure network server mentioned in the above paragraph.

Any publications or presentations that result from this research will not identify any subjects individually, and will present data in aggregate form only.

References

-

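### Does the cough arm need a single test-cough criterion and a written path for when the test cough fails?

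*Combined protocol and SAP*

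**What the plan says.** The protocol describes the cough method twice.

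- **Narrative under 'Procedure at time of IUD insertion'.** The subject gives one strong cough as a test. The next step opens "If provider is pleased by the strength of the" patient's cough; if so, she coughs again and the tenaculum is placed at that second cough. It adds: "Only one test cough will be allowed".
- **Provider script, 'Cough Method'.** The provider is told to "ask the patient to give a strong cough". It continues: "If you are pleased with the cough (cervix remained in view during cough), then ask the patient to cough once more". The tenaculum is closed during that next cough.

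Neither text says what to do otherwise. Two nearby instructions bear on this. The narrative opens with "A single-tooth tenaculum will be used in placement of all IUDs", and the script, before the two methods are set out, says "Place tenaculum on anterior lip of cervix in accordance to your randomized group".

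'Statistical analyses' compares the groups on pain by t-test or Wilcoxon test. It makes no exception for a subject whose test cough was unsatisfactory.

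**The concern.** The cough method is one of the two things the trial compares, so its description defines an arm. Read literally, the criteria can disagree. A strong cough that loses sight of the cervix satisfies the narrative and not the script; a weak cough that keeps it in view does the reverse. For a subject who does not pass, the text is silent.

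The setting makes that silence more noticeable. 'Randomization' states that "patients and providers will be aware of the group each subject is randomized to", and the same provider later rates satisfaction, a secondary outcome. The Introduction says that the two methods "are utilized by providers based on preference and/or their previous training". If a provider who dislikes the test cough falls back on slow closure, the arms become more alike, the expected difference shrinks and power falls. Handling that differs between providers could also enter the planned look at physician experience. The list under 'Data collection' names neither the test-cough result nor the method used, so a reader might never learn whether this had happened.

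**Working it through.** **1. How far the two texts conflict.**

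| Element | Narrative | Script |
|---|---|---|
| Cough requested | one strong cough | a strong cough |
| Who decides | provider, if pleased | provider, if pleased |
| What is assessed | strength | cervix still in view |
| Placement | at the second cough | at the second cough |
| Unsatisfactory test cough | not stated | not stated |

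They agree on the request, on who decides and on the placement. They differ only for a strong cough that loses the view or a weak cough that keeps it. The documents do not say how often either occurs.

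**2. What the surrounding text leaves open.** A tenaculum is used for every IUD, one test cough is permitted, and placement follows the allocated group. Placing the tenaculum at the next cough breaches none of these. Slow closure in a cough-arm subject departs from the last.

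**3. Size if slow closure happened anyway.** Stated in 'Sample size determination': difference 16 mm, power 90%, alpha .05, total 66. Assumed: 33 per arm, two-sided t-test, common SD.

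The SD is not stated, so 66 cannot be reproduced directly; the SD it implies can be found. With 64 degrees of freedom the critical t is 1.998, and 90% power needs a noncentrality of 3.291. Then

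SD = 16 / (3.291 × √(2/33)) = 16 / (3.291 × 0.2462) ≈ 19.75 mm.

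The normal approximation gives 16 / ((1.960 + 1.282) × 0.2462) ≈ 20.05 mm, so the planned size fits an SD near 20 mm.

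Suppose k of the 33 cough-arm subjects are closed slowly and have slow-arm pain. The expected difference is 16 × (1 − k/33), a loss of 16/33 = 0.48 mm for each.

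| k (assumed) | Expected difference | Power, SD 18 | Power, SD 19.75 | Power, SD 25 |
|---|---|---|---|---|
| 0 | 16.0 mm | 94% | 90% | 73% |
| 1 | 15.5 mm | 93% | 88% | 70% |
| 2 | 15.0 mm | 92% | 86% | 67% |
| 3 | 14.5 mm | 90% | 84% | 64% |

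The SD 25 column starts at 73% with no switching, so most of its shortfall below 90% comes from the SD. That is a separate matter. A simulation at SD 19.75 that allows for the extra spread of a mixed arm (60,000 runs) gave 0.901, 0.882, 0.856 and 0.835, in line with the middle column.

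**4. Direction of any error.** If the method makes no difference to pain, the expected difference is 0 × (1 − k/33) = 0 whatever k is. On these assumptions switching can hide a real difference but cannot create a false one.

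**5. What one wording and two recorded items would change.** The groups are already compared as groups. The sample size, test and outcome would stay the same. Recording the method would not recover lost power.

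**The case for a change.** The best case for acting is that it costs little. One shared wording and a note of the test-cough result and method used need no extra subjects or visits, and readers could then see how the cough arm was delivered. If placement follows the second cough regardless, the condition in the narrative has no function, and the text does not say that it follows regardless. Leaving this to people who know the allocation is untidy.

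Part of this stands. The wordings do differ, no alternative path is written, and the path in step 2 of the working is inferred from neighbouring instructions. A count of departures would be useful description.

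The rest is weaker. The Introduction's remark on provider preference describes ordinary practice, as the reason for doing the trial; inside the trial the script binds the provider to the allocation. The 'Data collection' list is plainly partial: it also omits BMI, GAD7 score, chronic pain and narcotic use, which the protocol says are collected. Its silence therefore shows little, and comparing groups requires the arm to be known. Providers rate satisfaction unblinded in both arms whatever happens at the test cough, so that weakness does not come from this gap. The effect on the physician-experience correlation is speculative and concerns an exploratory analysis.

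**Conclusion.** The concern is accurate about the text but does not call for a change to the plan. It is missing detail in how one arm is delivered, confined to test coughs that the two wordings would classify differently or that the provider finds unsatisfactory. Following the plan as written gives no wrong result: subjects are compared by assigned arm, and that comparison stays valid.

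The calculated loss is about 2 percentage points of power for each cough-arm subject closed slowly, from 90% to about 84% at three of 33. It rests on assumed switching counts, equal arms, an implied SD of about 19.75 mm and slow-arm pain in those subjects. It also requires the provider to depart from the randomized-group instruction. With no switching it is zero. For prompt closure without a cough the documents give nothing to calculate from.

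The narrative and script are for the investigator to reconcile as a point of editing; which criterion or path applies is not a statistical question. The sample size, outcomes and analysis do not depend on the answer.

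### The script's only prompt at completion asks for pain now, although the protocol says the rating at that point is overall pain, a named secondary outcome

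*Combined protocol and SAP*

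**What the plan says.** The last paragraph of the Introduction sets out the outcomes. Pain at tenaculum placement is the main comparison, provider satisfaction is a secondary outcome, and "Overall pain with IUD insertion will also be a secondary outcome".

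The narrative under *Procedure at time of IUD insertion* says when that outcome is collected: "All subjects will be asked to rate their overall pain at the completion of the procedure".

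The same section then gives a script for the provider to read aloud. It contains four pain prompts. The first comes when the subject is positioned: "I will tell you when to stop. On your scoring sheet, please mark your pain at this time". The second and third follow speculum placement and tenaculum placement. The fourth comes after this step: "Provider does: Sound uterus, place IUD, cut strings, remove speculum". Its full wording is "Provider says: On your scoring sheet, please mark your pain at this time".

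The visual analog scale is described under *Sample size determination* as "anchored by 2 verbal descriptors, one for each symptom extreme". Under *Statistical analyses* the plan for pain reads "We will compare groups on the primary outcome of pain using T-tests versus Wilcoxon test pending the normality of the results". A test is also named for provider satisfaction, but none specifically for overall pain.

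**The concern.** Pain at the moment the speculum has just come out and pain over the whole insertion are different quantities. The narrative asks for the second. The spoken prompt, taken at its word, asks for the first.

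By the fourth prompt the subject has heard the same sentence three times, each time meaning current pain, and nothing in the script signals that the question has become retrospective. Some subjects may rate what they feel then, some the whole procedure, and some a blend. A mark on a line does not record which question was answered, so if subjects did read the prompt differently, no later analysis could separate them. The slow-versus-cough comparison on this outcome might then not be a comparison of overall pain.

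**Working it through.** No arithmetic on effect size or power applies. Rewording a prompt changes none of the design figures (16 mm, 90% power, alpha 0.05, total 66). The check is a comparison of texts and some counts.

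**Step 1: ratings wanted against prompts given.** From *Procedure at time of IUD insertion*:

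| Point | Narrative asks for | Script asks for |
|---|---|---|
| Positioning | baseline pain | pain at that time |
| After speculum | pain at that point | pain at that time |
| After tenaculum | pain at that point | pain at that time |
| Completion, speculum out | **overall** pain | pain at that time |

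The first three rows agree. The fourth does not.

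**Step 2: is the fourth prompt meant to be the overall rating?** The document does not say so outright. I infer it because this is the only prompt after the procedure is complete, and because four prompts match the four ratings per subject in the narrative (baseline, speculum, tenaculum, overall).

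**Step 3: does the script ask for overall pain anywhere?** The prompt sentence occurs 4 times with the same words. The word *overall* occurs 2 times in the whole document, once in the Introduction and once in the procedure narrative. It occurs 0 times in the script. So 1 of 4 ratings is meant to be overall, and 0 of 4 prompts say so.

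**Step 4: does the scale supply the time frame?** As described, it has 2 verbal anchors, one for each extreme of intensity. Neither refers to a period. Only the spoken words or a label on the scoring sheet could tell the subject to rate the whole procedure, and the sheet is not in the document.

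**Step 5: both possibilities for the sheet.** If item four is labelled as overall pain, the provider's words conflict with the label or fail to support it. If it is not so labelled, nothing shown asks the subject for overall pain. The script line needs changing in both cases.

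**Step 6: extent.** One of two named secondary outcomes is affected, in at most 66 subjects. How many hear this English sentence is not given, because eligibility is "English or Spanish speaking" and no Spanish script is shown.

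**The case against.** The strongest reply is that every prompt directs the subject to a scoring sheet that we cannot see. An identical spoken line at four points fits a generic cue to make the next mark, with the sheet defining what each mark means. On that reading the time phrase says when to write, not what to rate, and a label saying *overall* on item four would leave only a tidy-up of wording. The description of the scale is also generic and does not specify this study's form, so its silence on time frame is weak evidence about the actual sheet. Nor does the protocol say that the script contains every question put to the subject. Finally, both arms hear the same words at the same point, so the randomised comparison stays like for like whatever is being rated.

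Much of this stands as a limit on the finding. The sheet may carry the right label, the link between the fourth prompt and the overall rating is inferred, and no difference between arms is claimed. It does not remove the conflict. A script exists to standardise what subjects are asked, and one that allows two readings at the point where a named outcome is collected does not do so. Balance between arms protects the comparison from bias between arms. It does not make the quantity compared the one that the protocol names.

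**Conclusion.** The concern holds. The script's prompt at completion does not ask for the rating that the procedure narrative assigns to that point, and the Introduction makes overall pain a secondary outcome. It should be fixed.

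The reach is limited. The primary outcome and sample size are unaffected, and no size or direction of bias is claimed. Because the analysis section names no test specifically for overall pain, the point concerns what the outcome means, not how it is tested.

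The conclusion assumes that the fourth prompt is the overall rating and that the script is read as written. How far the data would be affected depends on the label on the unseen sheet and on how subjects understood the words. My confidence is therefore medium.

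**What to change.** Reconcile the script with the procedure narrative. Change the last prompt to ask explicitly for the whole procedure, for example: *On your scoring sheet, please mark your overall pain for the whole procedure.* Make the label of the fourth scoring-sheet item say the same, and carry the wording into any Spanish version. Leave the first three prompts as they are, since current pain is what the narrative wants there.

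The cost is one script sentence and one label, repeated in any Spanish version. It adds no subjects, visits, ratings or time.

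### The primary comparison is unadjusted although GAD7 and a baseline pain mark are collected, so precision is given up (without bias) that a prespecified covariate-adjusted model would recover

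*Combined protocol and SAP*

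**What the plan says.** All references are to the combined protocol and SAP.

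- **Introduction.** Whatever the procedure, "anxiety, depression, and a woman's anticipation of the pain she will experience are strong predictors of the pain experienced". A separate sentence, limited to procedures that dilate the cervix and pass a device through the internal os, says that "a history of dysmenorrhea, nulliparity, and postmenopausal status are associated with increased pain".
- **Methods and Materials.** Nine items are collected before randomization: age, parity, race, education, number of cesareans, BMI, chronic pain history, daily narcotic use and GAD7.
- **Procedure at time of IUD insertion.** Each woman marks her pain four times: at the start, after the speculum, at tenaculum placement and at the end. The primary interest is pain at tenaculum placement.
- **Randomization.** The trial is unblinded, and the arm is disclosed at some point before the speculum is placed.
- **Statistical analyses.** "We will compare groups on the primary outcome of pain using T-tests versus Wilcoxon test pending the normality of the results". Patient characteristics enter only through a general sentence about looking for correlations with demographics and physician experience. No covariate adjustment is planned, and no stratified randomization is described.
- **Data collection.** The REDCap list names "age, parity, race, level of education", the pain responses and provider satisfaction. GAD7, cesareans, BMI, chronic pain, narcotic use and the assigned arm are not named.

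**The concern.** The plan identifies a strong predictor of the outcome, measures it before randomization, and then leaves it out of the comparison that decides the trial. A baseline pain mark is also taken and left unused. With a continuous outcome, a linear model that includes prognostic baseline values removes the variance they explain from the error term and corrects the estimate for chance differences between arms in those values. This needs no extra patients.

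What is at stake is precision. The trial has 66 women and no stated allowance for dropout, so there is little reserve if pain scores vary more than the design supposed. Naming the covariates in advance also removes the temptation to choose them after the data are seen, which the open-ended correlations sentence does nothing to prevent.

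A smaller matter is that the database list does not name GAD7, the covariate best supported by the Introduction.

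**Working it through.** **Inputs from the documents (Sample size determination).** Difference: "We have chosen a 16 mm difference on a standard 100-mm visual analog pain scale". Design: "detect at least a 16 mm difference with 90% power and alpha of .05". Size: "we estimated a total sample size of 66".

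**Assumptions.** The test is two-sided and allocation is 1:1, giving 33 per arm. The SD is not stated. R-squared (R2), the share of within-arm outcome variance explained by the baseline covariates, is not stated either and is shown at 0.10, 0.20 and 0.30.

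**Step 1: the plan's own figure.** Without an SD, 66 cannot be reproduced directly, so I solved for the SD it implies. By the normal formula, SD = 16 / [(1.960 + 1.282) × sqrt(2/33)] = 20.05 mm. Forwards, with SD 20: n per arm = 2 × 20² × (1.960 + 1.282)² / 16² = 32.8, rounded up to 33, or 66 in total. An SD of 20 mm is therefore consistent with the stated size. It remains an inference: a one-sided test would give 66 at an SD of about 22.

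**Step 2: the unadjusted test.** SE = 20 × sqrt(2/33) = 4.92 mm. Noncentrality = 16 / 4.92 = 3.25. Power from the noncentral t on 64 df is 89.3% (90.1% by the normal approximation). The 95% half-width is 1.96 × 4.92 = 9.65 mm.

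**Step 3: the adjusted model.** Residual SD = 20 × sqrt(1 − R2). The confidence interval narrows by 1 − sqrt(1 − R2).

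| R2 | Residual SD (mm) | SE (mm) | 95% half-width (mm) | Narrowing | Power at 16 mm |
|---|---|---|---|---|---|
| 0 | 20.0 | 4.92 | 9.65 | none | 89.3% |
| 0.10 | 19.0 | 4.67 | 9.16 | 5% | 92.1% |
| 0.20 | 17.9 | 4.40 | 8.63 | 11% | 94.7% |
| 0.30 | 16.7 | 4.12 | 8.07 | 16% | 96.9% |

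Two or three covariates reduce the df from 64 to 62 or 61. At these values that costs less than 0.1 percentage point of power.

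**Step 4: sensitivity to the SD.** If the SD is 25 mm, power at 16 mm from the same noncentral t is 72.6% unadjusted and 77.0%, 81.6% or 86.4% at the three R2 values. The gain is larger where the trial is weaker: about 4 to 14 points, against about 3 to 8 at SD 20.

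**Step 5: which collected values are clean covariates.**
- *GAD7* is collected before randomization and measures anxiety, which the Introduction calls a strong predictor.
- *The first pain mark* comes before the speculum. The plan does not say whether it also comes before the arm is disclosed, so that order must be fixed.
- *The post-speculum mark* is made after disclosure in an unblinded trial, so knowing the arm could influence it. It is not a safe baseline.
- *Parity* is collected before randomization, but the Introduction ties nulliparity to passage through the internal os. Tenaculum pain is marked before the uterus is sounded.

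**The case against.** The strongest reply is that nothing here is invalid. A randomized comparison without adjustment is unbiased, and its standard error already allows for chance imbalance. Adjustment is therefore a choice for efficiency, and at the design's own 16 mm it adds only about 3 to 8 points to roughly 89% power, under an SD and an R-squared that the documents do not give. All of this stands, and it limits the point to a recommendation.

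A second reply is that VAS scores may be skewed, which is why the plan keeps a Wilcoxon option, and a linear model should not ignore that. This also stands, and the fix provides for it.

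Stronger readings are tempting, and the documents do not support them:

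- **That GAD7 and four other items are discarded.** The privacy section says more generally that pertinent data go into REDCap, and paper records are kept until analysis is finished. The short list also leaves out the arm and physician experience, which the planned analyses need. It reads as an incomplete list. Parity and all pain marks are covered by it in any case.
- **That nulliparity is shown to predict the primary outcome.** The Introduction's statement concerns passage through the internal os.
- **That precision from anticipated pain is being lost.** The Introduction does name it as a predictor, but the plan never collects it. Asking for it would be an addition to the design.
- **That the last mark before the tenaculum is the natural baseline.** It follows disclosure of the arm, and adjusting for it could bias the arm estimate.

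**Conclusion.** The point holds as a loss of precision. The plan measures a predictor that it calls strong, and a baseline pain score, and uses neither in the primary comparison. Assuming an SD of 20 mm, 33 women per arm, a two-sided 5% test and an R-squared of 0.10 to 0.30, adjustment narrows the confidence interval by about 5% to 16% and lifts power at 16 mm from 89.3% to between 92.1% and 96.9%. The direction holds for any R-squared large enough to repay two or three degrees of freedom. The size cannot be fixed from the documents. If GAD7 and the first pain mark explain almost nothing, the gain is negligible, but so is the cost.

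A reader might infer that the unadjusted test biases the result, or that the database as described makes adjustment impossible. Neither follows. The mismatch between the two data lists is a drafting gap to close.

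**What to change.** 1. **Primary analysis.** Specify a linear model of the VAS mark at tenaculum placement on arm, adjusted for the first baseline VAS mark and GAD7. Parity may be added as an optional prespecified covariate. Report the adjusted mean difference with its 95% confidence interval.
2. **Timing.** State that the first pain mark and GAD7 are completed before the arm is disclosed. Do not adjust for the post-speculum mark.
3. **Non-normality.** Keep the planned t-test or Wilcoxon test as supportive. State in advance that robust standard errors or a rank-based ANCOVA will be used if the VAS is markedly non-normal, and by what criterion. Add a rule for a missing GAD7 or baseline mark.
4. **Housekeeping.** Make the REDCap list match the nine items in Methods and Materials, and add the assigned arm. Physician experience should also be listed, since its analysis is planned.
5. **Optional.** Add one VAS mark for expected pain, taken before the arm is known, as a further prespecified covariate.

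The cost is a few sentences of analysis text, some database fields, and two or three degrees of freedom. If item 5 is adopted, there is also one more mark per woman and one more degree of freedom. No additional patients are needed.
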